6.7 Treatment Delivery Schedule

- 6.7.1 Radiation treatments will be delivered in accordance with the standard radiation oncology clinic procedures. Treatment must be completed within the time frame of 5 to 14 calendar days, in which the first day of treatment will be considered day 1. The exact treatment schedule is left to the discretion of the treating physician.

6.7 Treatment Dose Schedule

Dose Level	2.1-4.0 cm diameter	4.1-6.0 cm diameter
1	7 Gy	6 Gy
2	8 Gy	7 Gy
3	9 Gy	8 Gy

7.0 THERAPY MODIFICATIONS

7.1 Dose Modifications

All prescription doses are determined in accordance with the previously described dosing schema. The index lesion will receive the current investigational dose, and all

other treated tumors will receive a previously demonstrated safe, standard of care dose prescription. No dose modifications are to be made outside of the selected dose prescriptions utilized in the study.

7.2 Concomitant Medication

- 7.2.1 All medications administered since protocol enrollment will be recorded in the medical record
- 7.2.2 No cytotoxic chemotherapies are to be administered during the administration of FSRT
- 7.2.3 Administration of pre-treatment or post-treatment corticosteroids (for example, dexamethasone 4-10 mg within 1 hour of radiation) is at the discretion of the treating physician.

7.3 Adverse Events (AE's) and Serious Adverse Events (SAE's)

- 7.3.1 Definition of Adverse Event (AE): Any untoward medical occurrence, which does not necessarily have a causal relationship with the study treatment. This includes any physical or clinical change experienced by the subject, whether or not considered related to the study treatment. An AE can therefore be any unfavorable or unintended sign, symptom, or disease temporally associated with the study treatment. Progression of the patient's cancer, including intracranial progression, is not considered to be an AE. AE's will be recorded in the medical record.
- 7.3.2 Definition of Serious Adverse Event (SAE): Any event occurring during the study evaluation period that results in any of the following outcomes:
 - Death attributed to treatment
 - Inpatient hospitalization
 - Any irreversible grade ≥ 3 CNS toxicity per the Common Terminology Criteria for Adverse Events (CTCAE) CNS toxicity criteria

All SAE's must be recorded in the medical record. The onset and end dates, severity, duration, effect on study administration (discontinuation/cancellation, for example), relationship to study treatment, and administration of any drugs or therapies to treat the SAE's will be recorded in the medical record.

7.4 Guidelines for adverse event recording

- 7.4.1 The Common Terminology Criteria for Adverse Events version 4.0 (CTCAE v4.0, http://evs.nci.nih.gov/ftp1/CTCAE/CTCAE_4.03_2010-06-14_QuickReference_5x7.pdf) will be used for grading adverse events.
- 7.4.2 The investigator must assess the relationship of any AE or SAE to the use of the study treatment using the following guidelines outlined in the table below:

Table 7.1 Attribution of Adverse Events

Code	Descriptor	Definition
5	Definite	The adverse event is clearly related to the investigational treatment
4	Probable	The adverse event is likely related to the investigational treatment
3	Possible	The adverse event may be related to the investigational treatment
2	Unlikely	The adverse event is doubtfully related to the investigational treatment
1	Unrelated	The adverse event is clearly not related to the investigational treatment

7.5 Monitoring of adverse events

Subjects having AE's or SAE's will be monitored with relevant clinical assessments and laboratory tests as determined by the subject's treating physician. All adverse events must be followed to satisfactory resolution or stabilization of the event(s). Any actions taken and follow-up results must be recorded in the subject's medical record. For all AE's or SAE's which require the subject to be discontinued from the study, relevant clinical assessments and laboratory tests will be repeated as clinically indicated, until final resolution or stabilization of the event(s).

7.6 Adverse event reporting

- 7.6.1 Notification of all SAE's must be reported to the Principal Investigator or his designee. A written report should be submitted to the appropriate Institutional Review Board (IRB) and UAB Clinical Trials Monitoring Committee per institutional policy.
- 7.6.2 Adverse events will be reported to the Clinical Trials Monitoring Committee.

7.7 Data and safety monitoring plan

- 7.7.1 This protocol will follow the UAB Data and Safety Monitoring Plan maintained by the UAB Comprehensive Cancer Center.
- 7.7.2 Serious adverse events will be reviewed in the UAB radiation oncology treatment planning or new patient conference, and the SAE's will also be reviewed by the Department of Radiation Oncology Quality Assurance committees.

7.8 Early Termination

Patients may be discontinued from the study prior to completion of study requirements for any of the following reasons:

- 7.8.1 The patient has a clinically significant adverse event as determined by the principal investigator.
- 7.8.2 The patient requests to be withdrawn from the study.
- 7.8.3 The patient fails to comply with the requirement for study evaluation/visits.
- 7.8.4 Other conditions for which, in the investigator's opinion, it is in the patient's best interest to be withdrawn from the study.
- 7.8.5 The patient did not meet eligibility requirements.

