8.0 STUDY PARAMETERS

- 8.1 For the purposes of this study, acute toxicity will be defined as event(s) that occur within 90 days of the completion of radiotherapy. Acute toxicity will be determined by both intra-treatment examinations and by scheduled follow-up evaluations after the treatment has completed. Late toxicity will be defined as any toxicity occurring > 90 days after the completion of treatment.
- 8.2 Baseline evaluations of enrolled patients must occur within four weeks of study enrollment.

Table 8.1 Required study evaluations

	Baseline	2 wk. post- FSRT	1 month	3 months	6 months	12 months
History and physical exam	x		x	x	x	x
Toxicity / AE evaluation		x ¹	x	x	x	x
Performance status (KPS)	x		x	x	x	x
MRI brain (Local & CNS control per protocol/RANO-BM)	x		x	x	x	x
FACT-Br (QOL evaluation)	x		x	x	x	x

¹ A 2 week post-treatment phone call will be made to the patient to see how they are feeling and evaluate if the patient is experiencing any toxicities.

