9.4 Follow-up

Enrolled patients will participate in a follow-up schedule as outlined in Table 8.1. Two weeks post- FSRT, the study coordinator will call the patient to assess how they are feeling and/or experiencing any toxicities. This will include a history and physical examination, performance status evaluation, MRI of the brain, and completion of the FACT-Br questionnaire at 1 month, 3 months, 6 months, and 12 months after completion of radiation treatment.

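### Section 7.8 lets an adverse event, visit non-compliance or the investigator's judgement end follow-up as well as treatment, which can selectively remove sicker patients from the secondary endpoints

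*Combined protocol and SAP*

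**What the plan says.** Section 7.8 opens with "Patients may be discontinued from the study prior to completion of study requirements for any of the following reasons". Its five grounds are:

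- 7.8.1: "The patient has a clinically significant adverse event as determined by the principal investigator". No grade, attribution or timing is attached.
- 7.8.2: the patient asks to be withdrawn.
- 7.8.3: "The patient fails to comply with the requirement for study evaluation/visits". No number of visits is given.
- 7.8.4: other conditions in which the investigator thinks withdrawal is best for the patient.
- 7.8.5: "The patient did not meet eligibility requirements".

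On treatment duration, section 6.7.1 says "Treatment must be completed within the time frame of 5 to 14 calendar days", with the first treatment day as day 1.

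On follow-up, Table 8.1 requires examination, toxicity evaluation, KPS, MRI and FACT-Br at each visit. Section 9.4 asks for "completion of the FACT-Br questionnaire at 1 month, 3 months, 6 months, and 12 months after completion of radiation treatment", with the examination, KPS and MRI at the same visits. Section 8.1 sets the late window: "Late toxicity will be defined as any toxicity occurring > 90 days after the completion of treatment".

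Section 7.5 requires adverse events to be followed until they resolve or stabilise, with results entered in the medical record. Where an event forces discontinuation, it adds repeat assessments and laboratory tests at clinical discretion.

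The statistical text in section 11.5 describes a descriptive, exploratory analysis summarised by dose level. The text reviewed contains no missing-data rule.

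**The concern.** In a trial of a treatment lasting two weeks at most, discontinuation from the study and discontinuation of treatment are different acts, and section 7.8 provides only for the first. A patient with a serious neurologic event at week 6 has finished FSRT. Discontinuing that patient under 7.8.1 or 7.8.4 has no effect except to end the scheduled assessments. The same applies to a patient too ill to attend who is discontinued under 7.8.3.

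Loss of this kind can be related to outcome. The endpoints exposed are late neurologic toxicity (11.2.2), local control (11.2.3), CNS disease control (11.2.4) and quality of life (11.2.5). Local control has a further dependence on later scans: under 11.2.3.1 an apparent increase in diameter is reclassified as a therapy effect only if subsequent imaging shows shrinkage, and a patient taken off study may not have that imaging.

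Section 2.5.1 acknowledges that dose escalation could raise toxicity. If it does, removals could differ between dose levels and blur the descriptive comparison.

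**Working it through.** **Step 1. What can be discontinued, and when.** FSRT ends by day 14 at the latest. The remaining study requirements are the two-week telephone call and the visits at 1, 3, 6 and 12 months. Late toxicity starts more than 90 days after completion, so it is captured mainly at 6 and 12 months, when no study treatment is left to stop.

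**Step 2. What section 7.5 retains.** Set against Table 8.1:

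| Item | Kept by 7.5 after discontinuation? |
|---|---|
| Adverse events already recorded | Yes, to resolution or stabilisation |
| Surveillance for new late events | Not required |
| Scheduled MRI | Not required |
| Scheduled KPS | Not required |
| Scheduled FACT-Br | Not required |

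**Step 3. The primary endpoint.** Section 11.1.1 counts DLTs within 90 days of the start of treatment. A week-6 event that meets the definition is already recorded, and later discontinuation does not erase it.

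**Step 4. Size.** The plan states no discontinuation rate, so there is no figure to reproduce and the following is illustrative.

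Inputs:
- Share removed, r: 6% to 20%. The lower value is the serious-toxicity rate in the centre's retrospective series (section 2.5.1: 4 of 72 patients, given as 6%), supposing every such patient were removed. The upper value is an assumption. Section 2.5.1 compares 25 and 30 Gy in five fractions, whereas this trial runs from 5 × 6 = 30 Gy to 5 × 9 = 45 Gy, so a rate above 6% is possible.
- Late-toxicity risk: 40% in removed patients, 10% in the rest (assumed).
- FACT-Br change: 15 to 25 points worse in removed patients (assumed).

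Formulas:
- True late-toxicity rate = r × 40% + (1 − r) × 10%. The observed rate is that of the retained patients, 10%.
- If retained patients have mean FACT-Br change m and removed patients have m − g, the true mean is m − r × g. The observed mean m is too favourable by r × g.

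| r | Patients of 30 | True late toxicity | Observed | FACT-Br error |
|---|---|---|---|---|
| 6% | 1.8 | 0.06 × 40% + 0.94 × 10% = 11.8% | 10% | 0.06 × 15 to 0.06 × 25 = 0.9 to 1.5 points |
| 20% | 6 | 0.20 × 40% + 0.80 × 10% = 16% | 10% | 0.20 × 15 to 0.20 × 25 = 3 to 5 points |

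The late-toxicity error is r times the risk difference. With a difference of 30 percentage points it is 1.8 to 6 percentage points. If removed patients had 20% risk instead of 40%, it would be 0.06 × 10 to 0.20 × 10 = 0.6 to 2 percentage points. If removal were unrelated to outcome, the expected error would be zero.

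**Step 5. Cross-check with another model.** Let p be the true rate, and w and v the shares of affected and unaffected patients removed before the outcome is recorded. The rate among retained patients is p(1 − w) / [p(1 − w) + (1 − p)(1 − v)]. At p = 20%:
- w = 25%, v = 10%: 0.15 / (0.15 + 0.72) = 17.2%.
- w = 75%, v = 0: 0.05 / (0.05 + 0.80) = 5.9%.

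The direction is the same. This model is harsher because it supposes removal before the late event is seen, and w and v are also assumptions.

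**The case against.** The strongest reply is that the clause is permissive, has five grounds, and comes with no discontinuation counts. The only losses described, the first three patients (section 11.5), were attributed to systemic progression or other illness judged unrelated to radiation, and are not described as removals under 7.8.1. Section 7.5 protects every recorded adverse event, not only the one that triggered discontinuation. The exposed endpoints are secondary and descriptive, with at most 30 patients per size cohort over three dose levels. All of this stands and limits the point, but none of it keeps a discontinued patient on the Table 8.1 schedule.

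Four stronger readings are tempting, and the documents support none of them.

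- A reader might infer that section 7.8 mainly removes the worst-affected patients. Without counts by reason, the text shows only that it can.
- A reader might infer that it hides the dose effect the trial seeks. Dose-finding rests on DLTs within 90 days, and those already recorded are unaffected. No formal dose-effect estimate is planned for late toxicity or quality of life.
- A reader might take 7.8.3 to mean that one missed visit is enough. No threshold is stated, so that is only its harshest reading.
- A reader might treat 7.8.5 as selection on toxicity. Ineligibility is not that.

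Finally, the text between sections 9.4 and 11.0 was not in the copy reviewed, and the institutional monitoring plan named in 7.7.1 is a separate document. An off-study follow-up rule in either cannot be excluded.

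**Conclusion.** The point holds as a wording defect with consequences for the secondary endpoints. As written, grounds 7.8.1, 7.8.3 and 7.8.4 can end scheduled assessment for reasons linked to the patient's condition, and section 7.5 closes only part of the gap.

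Under the stated assumptions the error is modest at 6% removed (1.8 percentage points for late toxicity, about 1 to 1.5 FACT-Br points) and material at 20% (6 percentage points and 3 to 5 points). Both depend on the assumed differences between removed and retained patients and shrink to zero if there are none. For local and CNS control neither the size nor the direction can be derived from the documents.

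This is not a finding that recorded DLTs or the dose decisions based on them are biased. The change is worth making because it is cheap and because lost late assessments cannot be recovered at analysis.

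**What to change.** Reword section 7.8 to separate two acts: stopping FSRT, which stays with the investigator as now, and ending follow-up.

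- Once any FSRT has been given, grounds 7.8.1, 7.8.3, 7.8.4 and 7.8.5 do not by themselves end follow-up. The patient stays on the Table 8.1 schedule to 12 months, as far as he or she is able, unless consent to follow-up is withdrawn or the patient dies. Ground 7.8.5 is included to retain safety data from treated patients.
- A missed visit is recorded as missed and the next one is attempted.
- Discontinuations are reported by reason and dose level.

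The cost is a wording amendment. The visits are already planned. The downside is some extra effort to follow sicker patients and more missing-visit records.

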8.0 STUDY PARAMETERS

- 8.1 For the purposes of this study, acute toxicity will be defined as event(s) that occur within 90 days of the completion of radiotherapy. Acute toxicity will be determined by both intra-treatment examinations and by scheduled follow-up evaluations after the treatment has completed. Late toxicity will be defined as any toxicity occurring > 90 days after the completion of treatment.
- 8.2 Baseline evaluations of enrolled patients must occur within four weeks of study enrollment.

Table 8.1 Required study evaluations

	Baseline	2 wk. post- FSRT	1 month	3 months	6 months	12 months
History and physical exam	x		x	x	x	x
Toxicity / AE evaluation		x ¹	x	x	x	x
Performance status (KPS)	x		x	x	x	x
MRI brain (Local & CNS control per protocol/RANO-BM)	x		x	x	x	x
FACT-Br (QOL evaluation)	x		x	x	x	x

¹ A 2 week post-treatment phone call will be made to the patient to see how they are feeling and evaluate if the patient is experiencing any toxicities.

9.0 EVALUATION CRITERIA

9.1 Pretreatment evaluations (baseline) will include the following:

- Complete medical history
- Physical examination including neurologic examination
- Vital Signs including weight
- Karnofsky performance status
- MRI of the brain
- Completion of FACT-Br questionnaire

To be eligible for enrollment, the patient must meet all inclusion criteria. Results of all baseline or screening evaluations, which assure that all inclusion and exclusion criteria have been addressed, must be reviewed by the investigator prior to enrollment of each patient. In addition, the patient must be thoroughly informed about all aspects of the study, including the study visit schedule, required evaluations, and all regulatory requirements for informed consent. Written informed consent must be obtained from the patient prior to enrollment.

9.2 Treatment delivery

9.2.1 All treatment plan dose distributions will be verified by UAB staff physicists and must meet the quality assurance standards set forth by the Department of Radiation Oncology prior to patient FSRT administration. Pre-treatment tissue phantom quality assurance checks will be completed. The phantom will be irradiated with the same plan as the patient including all couch angles and beam projections.

Once plans have met physics quality assurance parameters, treatment delivery will commence. Clinical treatment delivery feasibility will be determined by the ability of the patient to be set up accurately with confirmation of appropriate geometry on kilovoltage orthogonal imaging and cone beam CT imaging. Treatment delivery will be considered feasible if each set of pre-treatment set up images is approved by the treating physician(s) prior to administration of radiotherapy.

9.3 Treatment phase

- 9.3.1 The patient will be evaluated at least once by the treating physician during the time that he or she is undergoing radiation treatment.

9.4 Follow-up

Enrolled patients will participate in a follow-up schedule as outlined in Table 8.1. Two weeks post- FSRT, the study coordinator will call the patient to assess how they are feeling and/or experiencing any toxicities. This will include a history and physical examination, performance status evaluation, MRI of the brain, and completion of the FACT-Br questionnaire at 1 month, 3 months, 6 months, and 12 months after completion of radiation treatment.

11.0 STUDY ENDPOINTS

- 11.1 The primary endpoint of this study is to clinically assess early toxicity, specifically, to evaluate for the presence of a dose-limiting toxicity within 90 days of the initial treatment. We are interested in a risk of 20% or less.

- 11.1.1 The definition of a dose-limiting toxicity event will be the same as that used in RTOG 9005. It will be defined as an irreversible grade 3, any grade 4, or any grade 5 neurologic toxicity related to treatment that occurs within 90 days of the start of treatment. Since a patient may have more than one tumor treated the toxicity should be assigned to the tumor and not the patient if at all possible. Only 1 target per patient will receive the investigational dose prescription, and this target will be considered the index lesion. Any additional treated non-index lesion will receive a standard of care dose prescription that has previously been demonstrated to be safe.

11.2 Secondary endpoints include toxicity and efficacy assessments.

- 11.2.1 Determine the frequency and severity of acute neurologic toxicity.
- 11.2.2 Determine the frequency and severity of late neurologic toxicity.
- 11.2.3 Determine the rate of local tumor control with FSRT.
 - 11.2.3.1 The index lesion's treatment response will be assessed according to the RANO-BM criteria where a 20% increase in maximal diameter from nadir represents local tumor progression.³⁴ Additionally, the presence of more than scant tumor cells present at the time of salvage surgery will be considered a local tumor failure. An apparent increase in tumor diameter that is observed and found to subsequently decrease in size upon further imaging will be considered an effect of therapy rather than a local failure.
- 11.2.4 Determine the extent of central nervous system disease control in accordance with the Response Assessment in Neuro-Oncology (RANO) criteria for brain metastases.³⁴
- 11.2.5 Determine quality of life over time as assessed by the FACT-Br questionnaire.

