11.5 Dose Escalation and statistical considerations

11.5.1 The modified toxicity probability interval (mTPI) method with adjustment based on observed dose limiting toxicity (DLT) rate will be employed in decision making concerning dose escalation within each cohort investigated.³⁵ The assumptions to be applied in establishing the mTPI methodology are:

- Each specific tumor size cohort exploration may include up to 30 patients for a total enrollment of up to 60 patients.
- The MTD is defined to have 0.20 probability of toxicity.
- The acceptable variance around the MTD is ± 0.05 (i.e., the region of the MTD is 15% to 25% incidence of dose limiting toxicity).

The dose assignment recommendations for cumulative number of patients are presented in Table 11.1. The size of each patient cohort during the dose escalation phase of the study will be at least 3 patients. Once the initial three evaluable patients have cleared the DLT evaluation period then an mTPI design will be used to determine whether to escalate or de-escalate the dose. Up to 10 evaluable patients may be enrolled at a specific dose prior to making a final dose escalation/de-escalation decision. If the DLT rate of the current dose does not exceed the maximum permitted toxicity rate as defined by the mTPI, then we will evaluate the next dose level. Patients not evaluable for assessment of DLT may be replaced. For any subsequent cohort of patients, the recommended dose assignment action will be based on the total number of patients with DLTs in the current and prior cohorts treated at the same dose level. For example, if a cohort of 3 patients are treated at dose level 1 for the first time and one of them experiences a DLT, then the recommended action for the next cohort of patients will be to stay at the current dose level (S); if this recommendation is accepted, then the selected dose level for the next cohort of patients will be 1; if a total of 6 additional patients are treated at dose level 1 and there are no more DLTs observed, then the cumulative number of patients treated at dose level 1 is 9, and the cumulative number of patients with DLTs at dose level 1 is 1 out of 9, thus the recommendation would be to escalate the dose for the subsequent cohort (E).

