The dose escalation plan will allow enrollment of a three-patient cohort prior to the mTPI rule taking effect at the beginning of each dose level. Up to three patients can be enrolled at the beginning of each dose escalation level. Those three patients must be followed throughout the dose evaluation period (90 days). If one of those three patients develop a DLT, then cohorts of up to three additional patients may be treated at that dose level and be within the 90-day evaluation period at any given time. For example, if 1 out of the 3 patients develops a DLT, then patients 4-6 may then be enrolled. Patient 7

may be enrolled after patient 4 has been followed without toxicity for 90 days.

Dose-finding for a cohort may be stopped when one of the following criteria is met:

- The lowest dose level appears too toxic after at least 3 patients are dosed at that dose level.
- The maximum sample size in dose finding of 30 evaluable patients per cohort has been reached.
- A minimum of 10 evaluable patients have been treated at the estimated MTD.

Analysis will be descriptive and exploratory. Data will be summarized and listed by dose level. Toxicity, local tumor control local, central nervous system disease control in accordance with the Response Assessment in Neuro-Oncology (RANO) criteria for brain metastases, and QOL, will be presented in the form of patient data listings that include, but are not limited to, age, gender, dose, and tumor response at each visit. If the data permits, local tumor control rate, central nervous system disease control rate and corresponding exact confidence interval will be calculated. Additional exploratory data analysis will be performed as data permits.

Interim review of enrolled patients demonstrated that the first three patients were not evaluable at the timepoint for the primary endpoint due to systemic disease progression and/or other medical illnesses that were deemed to be unrelated to their radiation treatment. This was presented to the clinical trials monitoring committee, and it was decided that study continuation was appropriate; however, it was agreed upon that there should be enrollment of 6 patients at dose level 1 in the cohort of patients with tumors 2.1–4 cm in diameter prior to consideration of dose escalation in order to ensure safety. After this, dosing decisions will return to the originally proposed chart as displayed below.

Table 11.1 Dose Escalation rule of the modified toxicity probability interval method

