11.5 Toxicity rates

11.6.1 The primary endpoint of the study is to assess the rate of dose limiting toxicity experienced within 90 days of the completion of treatment. The maximum tolerated dose is defined to have a dose limiting toxicity rate of 20% or less. This will be assessed according to the mTPI method as described above.

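### Grade 3 neurologic toxicity counts as a DLT only if irreversible, but the plan has no rule for a grade 3 event still ongoing when the 90-day window closes and the dose decision is made

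*Combined protocol and SAP*

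**What the plan says.** Section 11.1.1 takes its DLT definition from RTOG 9005: "It will be defined as an irreversible grade 3, any grade 4, or any grade 5 neurologic toxicity related to treatment", occurring within 90 days of starting treatment. Grade 4 and 5 events count outright. Grade 3 events count only with the added condition of irreversibility.

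Section 11.5.1 sets the timing of the decision: "Once the initial three evaluable patients have cleared the DLT evaluation period then an mTPI design will be used" to choose the next dose. The text above Table 11.1 gives the evaluation period as 90 days. The design parameters are "The MTD is defined to have 0.20 probability of toxicity" and "The acceptable variance around the MTD is ± 0.05".

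Other provisions touch on ongoing events, but none says how to count them:

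- Section 7.5 has adverse events followed until they resolve or stabilise, without linking this to the DLT tally.
- Table 8.1 schedules visits at 1, 3, 6 and 12 months. Section 9.4 counts these from completion of radiotherapy.
- The SAE list in section 7.3.2 uses the same irreversibility condition. An ongoing grade 3 event is therefore an SAE only through hospitalisation or attributed death.

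The start of the window is stated in two ways. Section 11.1 says "to evaluate for the presence of a dose-limiting toxicity within 90 days of the initial treatment". The section headed Toxicity rates says the aim is to "assess the rate of dose limiting toxicity experienced within 90 days of the completion of treatment".

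**The concern.** The mTPI table needs a whole number of DLTs on the day the decision is taken. For a grade 3 event, that number depends on whether the deficit will later recover. Suppose a treatment-related grade 3 deficit begins on day 70 and is still present on day 90. The plan gives no duration, recovery criterion, adjudicator or adjudication date from which to classify it. One investigator could call it irreversible, another could call it not yet a DLT, and the two could reach different dose decisions from the same data.

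The literal reading errs in one direction: irreversibility has not been shown, so the event is left out and the count is lower. Groups are small enough for one event to change the action, and this count determines the primary objective, the MTD in each size cohort.

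**Working it through.** **Inputs.** From section 11.5.1: target DLT probability 0.20, interval 0.15 to 0.25, first decision after three evaluable patients. From the text above Table 11.1: six patients at level 1 of the 2.1-4.0 cm cohort before escalation is considered. Assumed, because the documents do not state them: a uniform Beta(1,1) prior, and a rule that a dose is unacceptable (DU) when P(p > 0.20) exceeds 0.95.

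**Step 1: reproduce the plan's worked example.** With d DLTs in n patients the posterior is Beta(1+d, 1+n−d). The action is the interval with the largest probability per unit length.

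| d/n | below 0.15 (E) | 0.15-0.25 (S) | above 0.25 (D) | Action |
|---|---|---|---|---|
| 1/3 | 0.1095/0.15 = 0.73 | (0.2617−0.1095)/0.10 = 1.52 | (1−0.2617)/0.75 = 0.98 | S |
| 1/9 | 0.4557/0.15 = 3.04 | (0.7560−0.4557)/0.10 = 3.00 | (1−0.7560)/0.75 = 0.33 | E |

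Both agree with the example in 11.5.1. The Table 11.1 cells for 0 to 3 DLTs in 3 to 8 patients, which are the cells used below, also agree.

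**Step 2: effect of one uncounted event.**

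| n | All counted | One uncounted |
|---|---|---|
| 3 to 8 | 1 DLT: S | 0 DLTs: E |
| 3 | 2 DLTs: DU | 1 DLT: S |
| 6 | 3 DLTs: DU | 2 DLTs: S |

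**Step 3: sensitivity of the escalation probability.** At n = 3 and at n = 6 the table escalates only with zero DLTs. If the true DLT rate is p and a share f of DLTs is unresolved and left out,

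P(escalate) = (1 − p(1 − f))^n.

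| True rate p | n | f = 0 | f = 0.25 | f = 0.50 |
|---|---|---|---|---|
| 0.30 | 3 | 0.700³ = 34% | 0.775³ = 47% | 0.850³ = 61% |
| 0.30 | 6 | 0.700⁶ = 12% | 0.775⁶ = 22% | 0.850⁶ = 38% |
| 0.40 | 3 | 0.600³ = 22% | 0.700³ = 34% | 0.800³ = 51% |
| 0.20 | 3 | 0.800³ = 51% | 0.850³ = 61% | 0.900³ = 73% |

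The n = 6 row applies to level 1 of the 2.1-4.0 cm cohort, assuming all six are evaluable. The values of p and f are assumptions; the documents give no rate of grade 3 events unresolved at day 90.

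**Step 4: the two window starts.** Treatment takes 5 to 14 calendar days with the first day as day 1, so completion falls 5 − 1 = 4 to 14 − 1 = 13 days after the start. The two 90-day windows therefore close 4 to 13 days apart. Because the 3-month visit is counted from completion, it can fall after a window counted from the start has closed. The last scheduled assessment that could inform the judgement may then come too late.

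**The case against.** A reader might infer that irreversibility can never be known by day 90, or that the rule cannot be applied at all. The text does not support that. Section 11.1.1 requires the toxicity to occur within 90 days; it does not say when permanence must be established. An early or plainly fixed deficit can be called irreversible inside the window. The difficulty is with late-onset or unresolved events.

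A reader might also infer that the plan is biased towards too high an MTD. That goes too far. What it means to clear the window is not defined, and an investigator could treat an unresolved event as irreversible, or the patient as not yet cleared. A one-step escalation probability does not establish bias in the final MTD either.

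There are real safeguards. Table actions are recommendations that may be declined. The tally is cumulative at each dose level, and nothing bars adding a DLT confirmed later. The staggering example has patient 7 wait until patient 4 has been followed free of toxicity for 90 days, though it is illustrated only after one DLT in three. Adverse events go to the monitoring committee, which has already slowed escalation once. These soften the consequences, but none tells the team what number to enter in the table.

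The definition is taken from RTOG 9005, whose working interpretation of irreversible is not available here. Even if one exists there, this plan does not state it.

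Finally, permanently counting every unresolved event would broaden the endpoint to which the 20% target applies. Suppose 10% of patients have true DLTs and another 10% have events that resolve slowly. Escalation after three patients would fall from 0.9³ = 73% to 0.8³ = 51%. This objection stands, and is why the change proposed below is provisional.

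**Conclusion.** The gap is real and should be closed. The plan makes a grade 3 DLT depend on irreversibility, takes the dose decision when the 90-day window closes, and leaves an event still ongoing then without a status. That one such event can change the action follows from the design parameters and agrees with Table 11.1; it needs no assumption about event rates.

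The escalation probabilities do need one. They show what happens if every unresolved event is left out, with the uncounted share set at 25-50%, and they do not forecast this trial. The three-patient figures do not apply to level 1 of the 2.1-4.0 cm cohort, where the six-patient figures (12% rising to 22-38% at a true rate of 30%) are the relevant ones. The documents support ambiguity whose literal reading favours escalation. They do not show that events will be missed or that the MTD will be overestimated.

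**What to change.** Add to section 11.1.1 that, for the mTPI tally only, a treatment-related grade 3 neurologic event with onset in the window and still grade 3 when the window closes is counted provisionally as a DLT. Remove it from the cumulative tally if later follow-up, including the 6- and 12-month visits, shows that it reversed. State what counts as reversal and who judges it. Keep the irreversible grade 3 definition for the final DLT rate, and report both tallies.

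Use one start for the 90 days throughout: sections 11.1 and 11.1.1 count from the start of treatment and the Toxicity rates section from completion, and these must be reconciled.

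The cost is a few sentences of text and an adjudication step at visits already scheduled. Some events that later reverse will be counted for a time, so escalation may be delayed; the size of that delay cannot be estimated from the documents.
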